### **4.2 Safety Population**

The Safety Population will include all patients who receive study drug during the Treatment Period. Patients in the Safety Population will be analyzed according to the actual dosing regimen received during the study.

## **5. STUDY PATIENTS**

### **5.1 Disposition of Patients**

Disposition will be summarized by randomized dosing regimen for all patients screened in the study. The following disposition information will be summarized (percentages based on the number randomized, with the exception of the reasons for discontinuation):

- The number of patients screened.
- The number of patients randomized.
- The number and percentage of patients treated within the Efficacy and Safety Populations.
- The number and percentage of patients who completed the study (defined as completing all study visits through Visit 11), completed Visit 10 and rolled into the open-label extension, and who completed 24 weeks of treatment but did not roll into the open-label extension and did not complete the safety follow up visit.
- The number and percentage of patients who prematurely discontinued, and the frequency and percentage of each discontinuation reason. The denominator for the percentage of each discontinuation reason will be the number of patients who discontinued.

Disposition and patient visits will also be presented for each patient in patient data listings. Patient data listings will list date of informed consent, date of first/last treatment, date of end of study/early termination, and reasons for discontinuation. A Kaplan Meier curve of time to study completion or early termination will also be presented. Patients who have completed the study will be censored.

### **5.2 Protocol Deviations**

Protocol deviations will be collected at both the site and patient level on the electronic Case Report Form (eCRF). A data review will be conducted before database lock by the sponsor to classify protocol deviations as minor or major. Deviations that may alter or confound interpretation of the study results will be classified as major deviations. Protocol deviations will be summarized by deviation classification and category for all randomized patients and listed by patient in a data listing.

## **6. DEMOGRAPHIC AND OTHER BASELINE CHARACTERISTICS**

Demographic characteristics (ie, sex, ethnic origin, race, date of birth, and calculated body mass index) will be collected at the Screening Visit, between Day -28 and -1, and detailed on the eCRF. Demographic characteristics will be summarized using descriptive statistics for all randomized patients.

Baseline characteristics will be summarized using descriptive statistics for all randomized patients and will include the following:

- baseline total SALT score.
- alopecia areata type (current episode; defined below).
- alopecia areata type (at disease onset; defined below).
- duration of current episode in months (calculated as: [date of randomization – date of current episode onset + 1] / 30.4375).
- duration of disease at onset in months (calculated as: [date of randomization – date of disease onset + 1] / 30.4375).
- current nail involvement.
- current eyelash/eyebrow involvement.
- current other facial hair involvement.
- prior Herpes Zoster vaccination.
- time since Herpes Zoster vaccination in months.

Other co-morbidities may be identified and included as baseline characteristics.

The patient's alopecia areata will be classified by the Investigator into one of three categories defined for this study:

- 1) Alopecia areata: patchy type hair loss,
- 2) Alopecia totalis or universalis: complete hair loss on the scalp with or without body hair loss,
- 3) Alopecia ophiasis: band-like hair loss limited to the periphery of the scalp along the back of the hair line in the occipital region and possibly extending over each ear in temporal regions.

The alopecia totalis and alopecia universalis category will be separated into each individual subtype for summaries. Alopecia areata category at baseline, defined as the current episode, and

alopecia areata category at disease onset will be summarized with the number and percent of patients in each category.

All demographics and baseline characteristics will also be listed within a by-patient data listing for all randomized patients.

Medical history will be summarized by frequencies of System Organ Class (SOC) and preferred term and will be coded using MedDRA Version 19.1. All medical history for each patient in the Safety Population will be included in a data listing.

## **6.1 Prior and Concomitant Medications**

Prior and concomitant medications will be summarized by WHO Drug ATC classification level 2 and preferred term and listed within a by-patient data listing.

Medications are classified as prior if the medication started and stopped prior to the first dose date of study drug or as concomitant if used on or after the first dose date of study drug. Concomitant medications will be recorded from Screening through the Follow-Up Visit at Week 28.

Partial and completely missing dates will be imputed for the purposes of classifying concomitant medications as follows:

- Partial dates will be imputed following the same algorithm as in Section 9.2 for Treatment-emergent adverse events (TEAEs).
- For an entirely missing start date (i.e. day, month, and year are missing), the start date will be set to the date of administration of study drug unless the stop date is prior to the date of administration of study drug, in which case the start date will be set to the stop date.

For an entirely missing stop date (i.e. day, month, and year are missing), the medication will be treated as ongoing.

## **7. MEASUREMENTS OF TREATMENT COMPLIANCE**

Patients will strive for 100% compliance with the daily dosing schedule. Treatment compliance will be summarized as time on treatment as well as percent of planned dose received for each dosing regimen. Time on treatment will be defined as date of last dose in the treatment period minus the date of first dose in the treatment period + 1. Percent of planned dose received will be calculated for the entire treatment period as follows:

$$100 * \frac{\text{Tablets Dispensed} - \text{Tablets Returned}}{\text{Tablets Expected}}$$

Tablets Expected is defined as the time on treatment multiplied by the expected number of active dose pills taken daily (x2 for the 8 mg BID group; x2 for the 16 mg QD group). Dose interruptions will be ignored in this calculation. Derived patient compliance, compliance per the eCRF (80% or higher versus less than 80%), and dosing exceptions will be listed in by-patient data listings.

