6.3 Study Design

This is a randomized, parallel group multicenter study to evaluate the efficacy and tolerability of two dosing regimens of CTP-543 (8 mg BID vs 16 mg QD), in adult patients with chronic, moderate to severe alopecia areata. Patients will be between 18 and 65 years of age and experiencing an episode of alopecia areata lasting at least 6 months and not exceeding 10 years, with at least 50% hair loss as measured by the SALT at Screening and Baseline, and are not concurrently being treated for alopecia areata with other treatments that might affect hair regrowth or immune response. Up to approximately 75% of alopecia areata patients with alopecia totalis or universalis, and no more than 10% with only alopecia ophiasis will be enrolled.

Patients may be screened up to 28-days prior to initiation of study drug. The Treatment Period is a 24-week dosing period where patients will be randomized to receive either CTP-543 8 mg BID, or CTP-543 16 mg QD and will be analyzed for the primary endpoints of the study. To minimize bias in the evaluation of study endpoints, patients, investigators, and site personnel will be unaware of the active drug dosing regimen by administering one 16 mg tablet and one placebo tablet 12 hours apart from each other for the 16 mg QD study group.

Figure 4: Study Design

Patients will provide informed consent prior to completing any screening procedures.

Patients will take the first dose of study drug in the clinic on Day 1. Patients will be instructed to take study drug every 12 hours. Patients should dose study drug in the clinic on all Study Visit Days after clinical laboratory blood draws are completed.

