8.4.1. Physical Description of Study Drug

Study drug will be CTP-543, a deuterated analog of ruxolitinib or an identical placebo tablet. Details regarding formulation and dosage are presented in [Table 4](#).

Table 4: Investigational Product

	Investigational Product (CTP-543 or Placebo)
Product Name:	CTP-543
Dosage Form:	Tablet
Dosage Strength of CTP-543	8 mg, 16 mg or placebo
Route of Administration	Oral
Physical Description	White, capsule-shaped tablets

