11.4.3. Study Drug Exposure

For each patient, the number of days of exposure to CTP-543 will be summed across the Treatment Period. The total number of days on study drug will exclude dose interruptions. The total number of days of exposure to CTP-543 will be summarized with the mean, standard deviation, median, minimum, and maximum number of days on the dose. Drug compliance will also be summarized.

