### **2.4 Treatment Regimens**

CTP-543 will be dosed orally as tablets. Doses and frequency will be allocated as follows:

- CTP-543 8 mg BID (every 12 hours)
- CTP-543 16 mg QD (16 mg in the morning and placebo tablet in the evenings)

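### SAP Section 7 counts interruption days that Protocol 11.4.3 excludes from exposure, and labels an all-tablet compliance ratio as active dose in the QD arm

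*SAP*

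**What the plan says.** **Exposure.** Protocol 11.4.3 asks for each patient's days of exposure and states: "The total number of days on study drug will exclude dose interruptions". It names drug compliance as a separate summary. SAP Section 7 defines time on treatment as last dose date minus first dose date plus 1, with no term for interruptions. For the compliance percentage built on that span it adds: "Dose interruptions will be ignored in this calculation". SAP Section 1 says that changes from the protocol's analyses will be documented in the SAP. SAP Section 12 lists one change only, the added absolute SALT thresholds.

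**Compliance ratio.** SAP Section 7 titles the ratio as a percentage of planned dose. The numerator is tablets dispensed minus tablets returned, with no split into active and placebo. The denominator is the product of that span in days and a daily count, which the SAP describes as "the expected number of active dose pills taken daily (x2 for the 8 mg BID group; x2 for the 16 mg QD group").

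SAP Section 2.4 gives the regimens as "CTP-543 8 mg BID (every 12 hours") and, for the other arm, "CTP-543 16 mg QD (16 mg in the morning and placebo tablet in the evenings"). Protocol 6.3 describes blinding by "administering one 16 mg tablet and one placebo tablet 12 hours apart from each other for the 16 mg QD study group". Protocol 8.4.1 counts both kinds of tablet as study drug: "Study drug will be CTP-543, a deuterated analog of ruxolitinib or an identical placebo tablet".

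**The concern.** On exposure, the two documents give different rules and the SAP does not acknowledge the difference. Protocol 8.2 ties dose interruption to hematologic thresholds and other adverse events. The patients whose days are overcounted are therefore those who stopped for tolerability reasons and later resumed. If interruptions were more frequent in one arm, a first-to-last span would hide the resulting difference in days on drug.

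On the ratio, the SAP credits the QD arm with two active tablets a day when it takes one, and calls the result a share of planned dose. In the BID arm each tablet is half the daily dose, so the title fits. In the QD arm the morning tablet carries the whole daily dose and the evening tablet none of it.

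The trial compares two ways of giving the same 16 mg daily total, and SAP Section 10 says that no pharmacokinetic endpoints are collected. The planned administration and compliance table (14.1.6) is where a reader would look to see whether the arms received the same amount of drug.

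**Working it through.** **Inputs.** The Treatment Period is 24 weeks = 24 × 7 = 168 days. The longest single interruption before discontinuation is 21 consecutive days (Protocol 8.2). The BID arm takes 8 mg morning and evening; the QD arm takes 16 mg in the morning and placebo in the evening. Missed-dose patterns are assumptions, because the documents give no data on when doses are missed.

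**1. The multiplier.** Counting all tablets, BID = 2 a day and QD = 1 + 1 = 2 a day, so the SAP's figure of 2 is reproduced in both arms. Counting active tablets, as the SAP labels it, BID = 2 but QD = 1, so the figure is not reproduced for QD. The number suits the all-tablet numerator; the word *active* does not. Replacing 2 by 1 for QD alone would give a fully compliant patient 100 × 336 / 168 = 200%.

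**2. Ratio against active dose, over 168 days.**

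- SAP ratio = 100 × (morning + evening tablets taken) / (2 × days)
- BID dose = 100 × (8 × morning + 8 × evening) / (16 × days)
- QD dose = 100 × (16 × morning) / (16 × days)

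| Assumed pattern | SAP ratio | BID dose | QD dose |
|---|---|---|---|
| Full compliance | 100% | 100% | 100% |
| 10% missed, morning and evening alike | 90% | 90% | 90% |
| 40% of evening tablets missed | 80% | 80% | 100% |
| 40% of morning tablets missed | 80% | 80% | 60% |
| All evening tablets missed | 50% | 50% | 100% |
| All morning tablets missed | 50% | 50% | 0% |

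The SAP ratio equals active dose in the BID arm under every pattern. In the QD arm it departs only when misses are uneven between morning and evening, and it can err in either direction.

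**3. Exposure days.** This is for a patient who resumes dosing and whose first and last doses span 168 days. SAP = 168; protocol rule = 168 minus interruption days; overstatement = 100 × (168 / protocol days − 1).

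| Interruption | SAP days | Protocol days | SAP too high by |
|---|---|---|---|
| 7 days | 168 | 161 | 4.3% |
| 14 days | 168 | 154 | 9.1% |
| 21 days | 168 | 147 | 14.3% |

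**4. Ratio after an interruption.** With 21 days off and otherwise perfect intake, the ratio is 100 × (2 × 147) / (2 × 168) = 87.5% in either arm.

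**The case against.** A reader might infer that the compliance formula is wrong and that the arms cannot be compared. The documents do not support that. Numerator and denominator both count every tablet, full compliance gives 100% in each arm, and tablet compliance is on one scale throughout. As a dose measure the arms diverge only under uneven misses. Nothing in the documents suggests that these are likely: the placebo tablet is described as identical and patients are kept unaware of the regimen.

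Some further inferences also fail.

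- *A QD patient taking 60% of active dose would pass the 80% compliance mark.* In SAP Section 7 that cut belongs to the separate eCRF compliance variable, and in Protocol 8.3 it triggers retraining at a visit. The derived whole-period ratio has no pass mark.
- *The 87.5% after an interruption is an error.* It is a defensible figure for the share of planned dose taken. The conflict with the protocol is about days of exposure.
- *Interruptions bias the comparison in themselves.* The rule is the same in both arms, so the comparison is distorted only if interruptions differ by arm. If a patient never resumes, the last dose precedes the gap and no off-drug days are counted.
- *The ratio obscures an adherence benefit of once-daily dosing.* Both arms take a tablet every 12 hours, so no compliance derivation could show one here.

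It can also be said that Section 7 concerns compliance, and that the table shells in Attachment A, which are not available here, may hold an exposure-days row. Interruptions do appear in Table 14.3.1.5 and in the dosing-exception and interruption listings. That softens the consequence. It does not supply a derivation: the SAP text defines no exposure variable other than the span.

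**Conclusion.** Two limited defects stand.

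The firmer one is exposure. The SAP's time on treatment contradicts Protocol 11.4.3, and the departure is not recorded. It adds 21 days (168 against 147, 14.3% too high) for a patient who resumes after one interruption of the longest permitted length, and proportionately less for shorter gaps. This assumes a 168-day span and that no exposure derivation exists outside the SAP text.

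The second is labelling. The ratio is sound as tablet compliance, but neither its title nor the word *active* is right for the QD arm. Read as dose, it is exact under even misses. Under the assumed loss of 40% of morning or of evening tablets only, it would be 20 percentage points too high (80 against 60) or too low (80 against 100).

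Both affect descriptive summaries only. Neither SAP analysis population depends on compliance or exposure, and no efficacy estimate changes.

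**What to change.** 1. In SAP Section 7, derive and summarise exposure days with interruption days removed, as Protocol 11.4.3 states. Keep the first-to-last-dose span only as a separately named duration. If the sponsor prefers to report the span alone, Section 12 must record that as a change.
2. Delete *active* from the definition of tablets expected and rename the ratio tablet compliance. Keep the multiplier of 2 in both arms. State that interruption days stay in the denominator.
3. If returned tablets are recorded by morning and evening position on the dosing card, add an active-dose percentage with numerator and denominator both limited to active tablets (one a day for QD, two for BID).

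Items 1 and 2 cost a few lines of SAP text and one extra derivation, provided that interruption dates are captured, as the protocol's rule presupposes. Item 3 may cost more. Protocol 8.4.3 shows that the cards carry time-of-day labels, but Protocol 8.4.5 does not require returns to be split that way, so new data capture could be needed. The derivation also needs the treatment codes and would be run after unblinding. If the split is not available, items 1 and 2 are sufficient.

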## **8. EFFICACY EVALUATION**

### **8.1 Primary Efficacy Endpoint**

The primary efficacy endpoint will be the relative change in SALT score for each dose regimen from baseline at Week 24.

#### **8.1.1 Severity of Alopecia Tool**

The SALT is a measure of hair absence that quantifies the amount of scalp surface without hair in a pre-specified quadrant of the scalp (right side, top, left side, back), that is further summed after applying a quadrant-specific multiplier indicative of scalp surface area contribution, to provide an overall score of total hair loss. Total SALT score is computed as  $[(\text{left quadrant raw score} \times 0.18) + (\text{right quadrant raw score} \times 0.18) + (\text{top quadrant raw score} \times 0.40) + (\text{back quadrant raw score} \times 0.24)]$ . The SALT assessment will occur via live examination of the patient during clinic visits.

As the SALT score is by nature a measurement of total surface without hair, it is important to note that in the context of this SAP, endpoints will follow these definitions:

- Absolute change = difference in SALT measurements (baseline SALT score minus follow-up SALT score)
- Relative change = percent change of the follow-up SALT score, where baseline SALT score is the denominator (i.e. absolute change divided by the baseline score, multiplied by 100)

### **8.2 Secondary Efficacy Endpoints**

Secondary efficacy endpoints include:

- Proportion of patients achieving at least a 90%, 75%, and 50% relative reduction in SALT score from baseline at Weeks 4, 8, 12, 16, 20, and 24;
- Absolute change in SALT scores from baseline at Weeks 4, 8, 12, 16, 20, and 24 in the Treatment Period;
- Relative change in SALT scores from baseline at Weeks 4, 8, 12, 16, 20, and 24 in the Treatment Period;
- Change in satisfaction of hair coverage as reported by patient

#### **8.2.1 Satisfaction of Hair Coverage**

Results of the patient satisfaction questions will be collected on Day 1 and at Week 24. Patients will answer the question “How satisfied are you with the hair coverage on your scalp today?”.

Responses range from 1-5 as follows: 1 (very dissatisfied), 2 (dissatisfied), 3 (somewhat satisfied), 4 (mostly satisfied), 5 (very satisfied).

### **8.3 Exploratory Efficacy Endpoints**

Exploratory efficacy endpoints include:

- Change in patient's eyebrows as measured by the patient's Visual Analog Scale (VAS);
- Change in satisfaction of hair coverage quality as reported by patient;
- Proportion of patients achieving an absolute SALT score of  $\leq 10$ ,  $\leq 20$ , and  $\leq 25$  at Weeks 4, 8, 12, 16, 20 and 24;

#### **8.3.1 Visual Analog Scale**

The VAS is a scale of continuous measure initially developed for pain that has been used in a variety of clinical settings where the endpoint of interest is based on a subjective perception. The VAS is a distinct 100 millimeter line anchored on the left end at full degree of impairment and on the right end at no degree of impairment, where indication of the degree of impairment perceived at the time of assessment is captured by marking the appropriate position on the line between the anchor points. The measured distance of the mark from the left anchor will be recorded in millimeters.

As specified in the Schedule of Events, patients will rate his/her eyebrows on the patient VAS. The left and right anchor points for the patient's eyebrow VAS are "None" and "Full", respectively. The patient VAS will measure the patient's eyebrows at the time of completion.

Since the VAS was measured right to left in terms on increasing impairment, the VAS analysis value will be calculated by taking 100 minus the collected value

#### **8.3.2 Satisfaction of Hair Coverage Quality**

Results of the patient satisfaction of quality questions will be collected on Day 1 and at Week 24. Patients will answer 7 questions with responses ranging from 1-5 as follows: 1 (very dissatisfied), 2 (dissatisfied), 3 (somewhat satisfied), 4 (mostly satisfied), 5 (very satisfied). The list of questions is provided in the protocol, Appendix 16.2.2.

## **8.4 Overview of Efficacy Analysis Issues**

### **8.4.1 Handling of Dropouts or Missing Data**

The Last Observation Carried Forward (LOCF) approach will be implemented for missing SALT score data, e.g., if the SALT score in the Week 16 visit window is missing, the next and closest available on-treatment SALT score measurement before the Week 16 visit window will be used for all remaining SALT assessments: Week 16, Week 20 and Week 24. Missing baseline values will not be carried forward. If a SALT assessment is missing between two non-missing SALT

assessments visits, the SALT score at that visit will be interpolated using the mean of the closest pre- and post-assessments.

If the number of discontinuations due to adverse events is substantial, other methods will be explored.

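### LOCF is the only pre-specified method for a missing Week 24 SALT score, with no sensitivity analysis, and its worked example is ambiguous beside the interpolation rule

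*SAP*

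**What the plan says.** The primary endpoint is defined in SAP section 8.1: "The primary efficacy endpoint will be the relative change in SALT score for each dose regimen from baseline at Week 24". Section 8.5.1 compares regimens on the mean of that quantity with 90% intervals. Protocol section 11.4.2 specifies a t-based 90% interval for the regimen difference. By the definition in SAP section 8.1.1, a positive relative change is an improvement.

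The protocol gives no missing-data rule and leaves statistical detail to the SAP. SAP section 8.4.1 contains four elements:

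- The general rule: "The Last Observation Carried Forward (LOCF) approach will be implemented for missing SALT score data".
- A worked example. Its trigger is "if the SALT score in the Week 16 visit window is missing". Its consequence is that the last on-treatment score before Week 16 "will be used for all remaining SALT assessments: Week 16, Week 20 and Week 24".
- An interpolation rule. Its trigger is "If a SALT assessment is missing between two non-missing SALT" visits, and then "the SALT score at that visit will be interpolated using the mean of the closest pre- and post-assessments".
- A contingency: "If the number of discontinuations due to adverse events is substantial, other methods will be explored".

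SAP sections 8.4 and 8.5 name no observed-case, likelihood-based or multiple-imputation analysis, and no sensitivity analysis.

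**The concern.** There are two separate issues.

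The first is the method. If SALT improves steadily on treatment, carrying an early score forward holds a dropout at a worse value than continued treatment would have given. The plan reports each regimen's Week 24 mean as well as the comparison, so both are exposed: the arm means whenever there is dropout, the difference when dropout is unequal. Equal dropout cannot be taken for granted. Comparing tolerability is part of the study objective, and protocol sections 7.3.1 and 8.2 discontinue patients whose dose interruption exceeds 21 consecutive days. Carried-forward values also enter the t-interval as if observed, so the interval does not reflect the uncertainty of the imputation. The only opening to another method has no threshold, names no method, and responds only to adverse-event discontinuations, although protocol section 7.3 lists several other reasons for withdrawal.

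The second is the wording. The worked example is triggered by one missing visit and does not say that the later visits are missing too. For a patient with Week 16 missing and Week 20 observed, the example and the interpolation sentence give different answers, and two programmers could implement them differently.

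**Working it through.** **1. Which rule can supply Week 24.** SALT is scheduled at Weeks 4, 8, 12, 16, 20 and 24. Interpolation requires a later non-missing score, and none is scheduled after Week 24. LOCF is therefore the only named rule for a missing primary value.

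**2. Dropout implied by the plan.** The plan has about 30 enrolled and 25 completers per arm (protocol sections 6.3 and 11.1), so implied non-completion is 5/30 = 16.7%. No SD, target interval width or dropout rate is stated, so the 25 cannot be rebuilt from a formula. The trajectories and SD below are assumptions.

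**3. Shortfall per dropout.** Assume mean relative improvement rises linearly from 0 to M at Week 24. A patient last seen at Week L is understated by M × (1 − L/24). With L spread evenly over 4, 8, 12, 16 and 20, the mean of L is 12 and the average shortfall is M/2.

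**4. Arm mean at 5/30 dropout.**
- M = 30: 5/30 × 15 = 2.5 points.
- M = 50: 5/30 × 25 = 4.2 points.

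With the same dropout, timing and trajectory in both arms, the bias in the difference is 0.

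**5. Regimen difference under unequal dropout.** Assume M = 45, so the average shortfall is 22.5, and no true difference.
- 10% vs 25%: (0.25 − 0.10) × 22.5 = 3.4 points.
- 10% vs 30%: (0.30 − 0.10) × 22.5 = 4.5 points.

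The bias runs against the arm with more dropout.

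**6. Scale.** Assume SD 38 and 30 per arm. The SE is 38 × √(2/30) = 9.8 and the 90% half-width is 1.672 × 9.81 = 16.4. The biases are 3.4/16.4 = 21% and 4.5/16.4 = 27% of it. Interval coverage falls from 90% to about 88% and 86.5% (non-central t, 58 df).

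**7. Imputed values counted as data.** At the same SD, 25 per arm gives 1.677 × 38 × √(2/25) = 18.0. Counting five carried-forward values per arm as observed shrinks this to 16.4, about 9% narrower.

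**8. The two sentences applied to one patient.** Assumed scores: baseline 88, Week 12 = 60, Week 16 missing, Week 20 = 40, Week 24 = 30.

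| Reading | Week 16 | Week 20 | Week 24 | Week 24 relative change |
|---|---|---|---|---|
| Worked example, literal | 60 | 60 | 60 | (88 − 60)/88 = 31.8% |
| Interpolation, observed scores kept | (60 + 40)/2 = 50 | 40 | 30 | (88 − 30)/88 = 65.9% |

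The patient is a 50% responder at Week 24 on one reading and not on the other. The effect on an arm mean is small: assuming a linear rise to 40, one such patient in 30 moves it by (40 − 20)/30 = 0.7 points.

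**9. Early Termination.** The Schedule of Events gives the Early Termination visit the Week 24 column, and protocol section 7.3.1 has early leavers complete all Week 24 assessments. SAP section 8.4.3 analyses scheduled visits at their nominal timepoint. An early SALT could therefore be filed as an observed Week 24 value and could trigger interpolation of the skipped visits. A mixed model fed that value would keep the bias.

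**The case against.** The strongest reply on wording is that the general rule covers only missing scores, under a heading about dropouts, so the example most naturally describes a patient with no later SALT. On that reading the two rules do not overlap and no observed score is touched. This stands. A reader might infer that the SAP orders observed Week 20 and 24 scores to be discarded; the documents do not support that. What remains is an example that omits the condition it needs.

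On bias, the reply is that the only dropout figure in the plan is the same for both arms, that both arms receive the same total daily dose, and that the 4 mg and 8 mg twice-daily cohorts of the earlier study are described as generally well tolerated. This also stands as far as it goes. Nothing in the documents shows that dropout will differ by regimen, so a reader should not infer that LOCF necessarily distorts the comparison. Nor is a trajectory given: the responders-by-visit figure is not shown. Rising regrowth is inferred from zero change at baseline and from 47% of the earlier 8 mg twice-daily cohort reaching a 50% reduction.

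On consequence, the trial is descriptive, with no test or margin, and the contingency says other methods will be explored, not substituted. That limits the weight of the point without removing it, because the estimate and its interval are the result.

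One might also fault interpolation over consecutive gaps, where every missed visit receives the same mean. That affects secondary visits only. For a single gap on the four-weekly schedule the mean is already linear in time.

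**Conclusion.** The point holds in limited form. LOCF is the sole pre-specified method for a missing Week 24 SALT score and is accompanied by no sensitivity analysis. If regrowth rises over time, it lowers each arm's Week 24 mean relative to continued treatment even with equal dropout. Bias in the regimen difference requires unequal amount or timing of dropout, and under the splits examined it is about a fifth to a quarter of the interval half-width. These sizes rest on assumed linear regrowth, evenly spread last visits and an SD of 38; none of these is in the documents. The interval is also somewhat too narrow because imputed values count as observations.

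The worked example is a drafting ambiguity to remove before programming. This is an improvement worth making before database lock; it does not invalidate the trial.

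**What to change.** - **Primary estimate.** Pre-specify the Week 24 regimen difference with 90% CI from a mixed model for repeated measures on relative change at all SALT visits, with regimen, visit, regimen-by-visit, baseline SALT and subtype stratum. State the covariance structure and a fallback. Keep LOCF and observed-case analyses as sensitivity analyses. Update SAP section 8.5.1 and Table 8-1, and record the change in SAP section 12.
- **Imputation rules.** State that an observed score is never replaced, that LOCF applies only when no later score exists, and that interpolation applies only when one does. Reword the example to say that Weeks 16, 20 and 24 are all missing.
- **Early Termination.** Map the Early Termination SALT to the visit nearest its actual date instead of nominal Week 24. Say whether a score taken after dosing stopped is used, since section 8.4.1 limits carried-forward scores to on-treatment ones.
- **Contingency.** Replace the open-ended sentence with the named analyses above.

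The cost is SAP text and modest programming before lock; the visits are already collected. The downsides are that a covariance structure must be chosen for about 60 patients, and that the model assumes data are missing at random and estimates the outcome as if treatment had continued. The SAP should say that this is the question intended.
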